Aim 4 (secondary outcome): Theta oscillations in frontal cortex are hypothesized to play a causal role in precision of working memory representations. During the probe, the participant responds with a specific color from a comprehensive color wheel. Plus or minus 15 degrees around the color wheel is considered "correct." For the correct trials, the precision is calculated as the distance in degrees from the response of the participant to the actual color of the memory item. To investigate if theta oscillations play a causal role in precision, the impact of theta stimulation on precision relative to arrhythmic and as a function of visual field will be investigated.

Aim 5 (secondary outcome): Stimulation that is aligned to the endogenous activity of the brain is hypothesized to entrain neural activity. Inter-trial phase coherence (ITPC) quantifies alignment of neural oscillations across trials. Stimulation in frontal-theta and parietal-alpha is proposed to increase ITPC in a frequency specific manner relative to control stimulation.

*Phase Two Overarching Goal:* Investigate the causal role of in-phase theta-frequency between frontal and parietal cortex in the prioritization and suppression of working memory representations.

Aim 6 (primary outcome): Stimulation that is delivered in-phase to frontal and parietal cortex in the theta frequency is hypothesized to increased working memory capacity relative to anti-phase theta stimulation. Working memory capacity is quantified using Pashler's metric.

Aim 7 (primary outcome): Stimulation that is delivered in-phase to frontal and parietal cortex in theta frequency is hypothesized to increase functional connectivity between the regions in a frequency specific manner. Functional connectivity will be measured using weighted phase lag index. In addition, we hypothesize that in-phase theta frequency stimulation will increase WPLI magnitude for retro-cues to the right visual field greater than the increase for stimulation with a retro-cue to the left visual field. This hypothesis is motivated by the finding that the left hemisphere processes information for the contralateral visual hemifield and that theta oscillations are linked to the active processing of information.

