#### 4.1 TREATMENT ASSIGNMENT PROCEDURES

Phase one: Participants will receive stimulation to either the frontal or parietal cortex in a randomized and counter-balanced sequence for the fourth and fifth session. Randomization and counterbalancing is performed by a script that generates a spreadsheet to stimulation ID mapping. Participants are randomized upon entering the fourth session of the experiment. Thus, there is no influence of the experiment on which sequence the participant will receive. Stimulation types are randomized and counter-balanced by a script at the time of the session and defined as theta, alpha, arrhythmic-theta, and arrhythmic-alpha. It should be noted that all analyses are controlled by a within-session contrast that accounts for general sequence effects.

Phase two: Participants are randomized to receive stimulation to both the frontal and parietal cortex in either theta or alpha frequency for both of the fourth and fifth session. A similar randomization procedure will be used as in phase one. Stimulation types are randomized and counter-balanced within a session by a script: in-synchrony, anti-synchrony, arrhythmic-synchrony, and arrhythmic-independent. It should be noted that all analyses are controlled by a within-session contrast by comparing to arrhythmic stimulation.

The primary analysis of the experiment is controlled within-session as a contrast with the arrhythmic control conditions. The difference in site of stimulation for phase one and the auditory difference between theta and alpha stimulation (theta is audibly slower than alpha) precludes double-blinding as the researcher will be aware of this difference in running the experiment. In other words, the study cannot be blinded and there is no attempt to blind the study. Furthermore, the control for each stimulation condition is self-contained within each session. The stimulation sessions for each phase consists of four stimulation conditions (described above) and two task conditions (retro-cue to the left visual field and retro-cue to the right visual field), thus there are a total of 8 conditions total for phase 1 and 4 conditions total for phase 2. With 600 trials per session, then will be 75 trials of each condition for phase 1 and 150 trials of each conditions for phase 2. The order of these trials is randomized for each session for each participant via a script.

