Aim 2 (primary outcome): Stimulation is hypothesized to increase the targeted frequency of stimulation relative to arrhythmic stimulation. This aim will provide evidence of target engagement, i.e. that stimulation is effective at modulating the targeted rhythm. Using Morlet wavelet convolution, the amplitude of theta and alpha oscillations will be estimated during task performance. The average across trials for each conditions will be calculated and baseline corrected using decibels to the time before the encoding array (700 to 300 milliseconds). Then, the average amplitude within the individual theta (ITF  $+$ /- 1 Hz) and alpha frequency (IAF  $+$ /- 1 Hz) band will be calculated for the second half of the train of TMS pulses. Previous research has shown that amplitude increase from stimulation increases over the course of the TMS train. Frontal-theta and parietal-alpha amplitude values will be submitted to a two-way repeated-measures ANOVA with TMS frequency by TMS site. We hypothesize to find a significant interaction ( $p < 0.05$ ) between TMS site and TMS frequency such that theta amplitude in frontal cortex increases greater for TMS to frontal in theta frequency and alpha amplitude in parietal cortex increases greater for TMS to parietal cortex in alpha frequency. Post-hoc t-tests will be performed using Tukey's method to control for multiple comparisons. *Sensitivity analysis*: To understand the specificity of this effect, the time-course for the impact of stimulation of amplitude will be plotted as well as the topographic plot for our effects. Cluster analysis will be used to estimate the spread of our effect in time and space. These analyses provide evidence to the robustness of the

impact of stimulation on amplitude.

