**Aim 7 (primary outcome):** Stimulation that is delivered in-phase to frontal and parietal cortex in theta frequency is hypothesized to increase functional connectivity between the regions in a frequency specific manner. Functional connectivity will be measured using weighted phase lag index (WPLI). To calculate WPLI, first Morlet wavelet convolution is performed to extract instantaneous phase and amplitude for the frequency of interest for the two target sites. Next, the cross-spectral density is calculated (one signal multiplied by the complex conjugate of the other). From the cross-spectral density the imaginary component of the resulting signal is extracted. Then those imaginary values are averaged over the time frame of instance (here, the second half of the stimulation train). Finally, the magnitude of the resulting vector is taken to be the WPLI. This metric quantifies the consistency of phase lag between the two target regions and is weighted towards signals with a 90 or 270 degree offset to address a common confound in EEG, volume conduction. We hypothesize that in-phase theta-frequency stimulation will increase theta-frequency WPLI strength between frontal and parietal cortex. In addition, we hypothesize that in-phase theta frequency stimulation will increase WPLI magnitude for retro-cues to the right visual field greater than the increase for stimulation with a retro-cue to the left visual field. This hypothesis is motivated by the finding that the left hemisphere processes information for the contralateral visual hemifield and that theta oscillations are linked to the active processing of information. Using a two-way ANOVA with factors for TMS frequency (theta or alpha) and retro-cue direction (left or right), we hypothesize a significant interaction ( $p < 0.05$ ) between TMS frequency and retro-cue direction such that WPLI magnitude is the greatest for theta-frequency stimulation with a retro-cue to the right visual field. Post-hoc t-tests will be performed using Tukey's method to control for multiple comparisons. *Sensitivity analysis:* The frequency, topographic, and spatial specificity of these effects will be explored. Similar to Aim 2, the time-course of WPLI can be estimated using a sliding window to demonstrate if functional connectivity rises and peaks at the end of the stimulation train. Furthermore, the topographic increase in functional connectivity will be quantified across the scalp to see if the effect is specific to the targeted regions. Finally, the frequency specificity will be explored by calculating functional connectivity across the full spectral range (2-30 Hz) and the specificity of connectivity changes in frequency domain will be displayed. Together, these analyses will establish the robustness

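### Aim 7 names WPLI, but its written steps leave out the normalising denominator, so the quantity they define scales with amplitude

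*Combined protocol and SAP*

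**What the plan says.** WPLI appears in the List of Abbreviations, in Section 2.3 ("Functional connectivity will be measured using weighted phase lag index") and in Section 11.1 under Aim 7. Only Section 11.1 says how to compute it. A Morlet wavelet step extracts phase and amplitude at the two target sites. The cross-spectrum is formed and its imaginary part taken. Next, "Then those imaginary values are averaged over the time frame of instance (here, the second half of the stimulation train"), and last, "Finally, the magnitude of the resulting vector is taken to be the WPLI". No step divides by mean|Im(S)|, and the signals are not reduced to unit vectors, as they are for inter-trial phase coherence in Aim 5.

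The plan then says of the result: "This metric quantifies the consistency of phase lag between the two target regions". It makes two predictions. One is an overall rise: "We hypothesize that in-phase theta-frequency stimulation will increase theta-frequency WPLI strength between frontal and parietal cortex". The other is an interaction of TMS frequency with retro-cue direction, and this is the only effect for which Aim 7 specifies a test. All Phase Two analyses use the difference from the matched arrhythmic condition.

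On amplitude, Aim 2 in Phase One states: "Stimulation is hypothesized to increase the targeted frequency of stimulation relative to arrhythmic stimulation". No Phase Two aim measures amplitude. Aim 7's sensitivity analyses ("The frequency, topographic, and spatial specificity of these effects will be explored") recompute connectivity over time, scalp and frequency.

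**The concern.** The name and the recipe for a primary outcome disagree, and the plan does not say which governs. One analyst working from the name and another from the steps would report different quantities: one bounded between 0 and 1, the other unbounded and in units of squared amplitude. Only the first is scaled so that a pure change of amplitude leaves it alone, which is the property the plan claims for its metric.

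This matters because the plan expects rhythmic stimulation to change amplitude relative to the arrhythmic control. If the steps are followed literally, a rise in the written quantity under in-phase theta stimulation could reflect stronger oscillations, more consistent phase lag, or both. Phase Two has no amplitude analysis to help separate them.

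**Working it through.** The documents give no value, effect size or power for Aim 7, so there is no figure to reproduce. The check is algebraic. Gains, lags and noise levels below are assumptions.

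**1. What the steps define.** With amplitudes a1 and a2 and phase difference d:
- S = a1·a2·exp(i·d), so Im(S) = a1·a2·sin(d).
- Written quantity: M = |mean(a1·a2·sin d)|.
- WPLI: W = |mean Im(S)| / mean|Im(S)|.

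**2. Scaling.** Multiply the amplitudes by g1 and g2, leaving the lag distribution alone. M becomes g1·g2·M. In W the factor cancels.

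| Gain | M multiplied by | Change in M |
|---|---|---|
| x1.1, both sites | 1.1 × 1.1 = 1.21 | +21% |
| x1.25, both sites | 1.25 × 1.25 = 1.5625 | +56% |
| x1.25, one site | 1.25 × 1 = 1.25 | +25% |

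A simulation with mean lag 45 degrees, phase SD 1 radian and Rayleigh amplitudes agrees. At x1.1 at both sites M went from 0.675 to 0.817, a ratio of 1.21. W stayed at about 0.674.

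**3. Subtracting the control.** Rhythmic minus arrhythmic is g1·g2·M − M = (g1·g2 − 1)·M. This is non-zero whenever the amplitude product differs between conditions.

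**4. Direction.** For lags spread symmetrically about a mean lag, M is proportional to g1·g2·sin(mean lag). Aim 8 predicts that in-phase stimulation reduces the lag. Starting from an assumed 45 degrees (sin = 0.707):
- Gain x1.25 at both sites is cancelled when sin(lag) = 0.707 / 1.5625 = 0.453, a lag of about 27 degrees.
- Gain x1.1 is cancelled when sin(lag) = 0.707 / 1.21 = 0.584, a lag of about 36 degrees.

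A larger fall in lag makes M go down despite the gain.

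**5. The declared interaction.** Let M_L and M_R be the arrhythmic values for left and right cues, and h_L and h_R the factors by which rhythmic stimulation multiplies them. The cue contrast within a participant is (h_R − 1)·M_R − (h_L − 1)·M_L. It is zero when both pairs are equal. With M equal, gains of x1.15 (left) and x1.25 (right) leave (0.5625 − 0.3225)·M = 0.24·M. With equal h, it is (h − 1)·(M_R − M_L).

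A simulation assumed 24 participants per frequency arm, 150 trials per cell (Section 4.1 gives "150 trials of each conditions for phase 2"), no change in coupling and no mean gain in the alpha arm. With equal gain of x1.1 or x1.25 for both cues, the interaction test rejected in 4–5% of runs for M and for W.

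**6. What the denominator does not remove.** With assumed lag 45 degrees, phase SD 40 degrees, gain x1.25 at both sites and unchanged coupling, M goes from 0.61 to 0.95 at every noise level tried. W stays at 0.87 without noise, but goes from 0.65 to 0.72 with independent site noise of 0.75 times the signal, and from 0.35 to 0.45 at 1.5 times. A better signal-to-noise ratio raises W even when true coupling is constant.

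**The case against.** The strongest reply is that WPLI is a named method. The plan names it repeatedly and describes it as phase-lag consistency, and its prose is loose enough (it calls a mean of real numbers a vector) to read as a compressed account of the standard index. The analysis software may well apply the denominator. That stands: the omission does not show that a wrong metric will be computed. It does leave a primary outcome with two incompatible definitions.

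A reader might also infer that Aim 7's declared test has an inflated error rate, or that amplitude gain would be reported as connectivity. The documents support neither:
- Equal gain does not inflate the declared interaction, and the documents give no values for any difference by cue.
- Very high rejection rates can be simulated for the overall theta rise: 99–100% for M at gain x1.25 and a fixed 45-degree lag. They come from a one-sample test that the plan does not name. If the lag falls to 27 degrees, upward rejection at the same gain is about 2%.
- Aim 2 concerns single-site stimulation in Phase One, with frontal theta and parietal alpha as its operative predictions. Aim 1 treats parietal theta as mismatched. Gain at both sites in theta is therefore not clearly what the plan expects, and one-site gain gives 25%, not 56%.

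Finally, the denominator leaves the signal-to-noise effect in place. This is correct. It is a reason to report amplitude as well, not to leave the formula incomplete.

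**Conclusion.** The definition is wrong as written and should be fixed before analysis. The steps for Aim 7 yield a quantity proportional to the product of the two sites' amplitudes. It does not by itself measure consistency of phase lag, and no other section supplies the normalisation. That conclusion is algebraic and rests on no assumed value.

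The consequence is conditional. If the steps are followed literally, the predicted overall rise in theta WPLI could be confounded with amplitude, by 21% or 56% for illustrative rises of 10% or 25% at both sites with lag unchanged. The actual gain and lag are not in the documents, so neither the size nor the sign of a bias can be stated. The declared frequency-by-cue interaction is affected only where gain, amplitude or lag differs by cue.

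**What to change.** In Section 11.1, Aim 7, make these changes:
- Define WPLI = |mean Im(S)| / mean|Im(S)|, or name the debiased form. Compute it in each condition, then take rhythmic minus arrhythmic.
- State whether the mean is over trials, time or both. The present text mentions time only. Once the denominator is added this matters: if the lag stays on one side of zero throughout a window, Im(S) keeps one sign and the ratio is exactly 1. At the 200 ms theta interval in Section 6.2, five pulses span 4 × 200 = 800 ms, so the second half is 400 ms, or two cycles.
- Report the rhythmic-minus-arrhythmic amplitude change at both sites, by cue, beside the WPLI result. Say that normalising removes direct amplitude scaling but not signal-to-noise effects.

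The cost is one formula, a sentence or two and one descriptive table. Aim 7's wavelet step already extracts the amplitudes, so no new data are needed. The angle range for phase lag in Aim 8 is also unstated; that is a separate wording clarification and does not bear on this point.

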### 3 PARTICIPANT SELECTION AND WITHDRAWAL

A total of 200 participants will be recruited for this study and all data will be collected at UNC-CH. No specific plans have been made to enroll participants from vulnerable populations. We will collect data until 48 participants have completed the final session for each phase, and we have estimated 100 participants per phase based on our criteria to progress to future sessions and the relatively large time commitment.

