### 11.1 STATISTICAL ANALYSIS STRATEGIES

The statistical analysis plan below aligns with the aims that are described in Section 2.3. all statistical estimates of population parameters will be tabulated along with corresponding confidence intervals (CIs) to convey levels of precision / imprecision. All hypothesis tests that yield large p-values ( $p>0.05$ ) will be reported as being inconclusive.

*Phase One* overarching goal: Investigate the causal role of frontal theta and parietal alpha oscillations in the prioritization and suppression of working memory representations. To control for non-specific effects of rhythmic TMS, we will use an active control: arrhythmic TMS (randomized inter-pulse-interval) that is matched to the target stimulation in number of pulses and temporal duration. All analyses will be performed on the difference from condition-matched arrhythmic TMS. The key analyses are built upon a three-way parallel arms design: with factors TMS frequency (theta versus alpha), location (frontal versus parietal), and cue direction (left versus right retro-cue). There is an equal number of trials for each of these conditions and there are 75 trials for each condition per participant.

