forms of arrhythmic stimulation are used: arrhythmic-in-synchrony stimulation delivers simultaneous stimulation to the two sites, but there is no consistent frequency component to the stimulation. Thus, activity in the two sites may be synchronized but not in a frequency-specific manner. The second control condition for stimulation is arrhythmic-independent where two trains of TMS are delivered in random patterns. There is no synchronization between the two pulse trains. Arrhythmic-independent controls for frequency and synchrony specificity of stimulation. All analyses will be performed on the difference from condition-matched arrhythmic TMS (in-phase minus arrhythmic-in-synchrony and anti-phase minus arrhythmic-independent). The key analyses are built upon a three-way design: with factors TMS frequency (theta and alpha), TMS alignment (in-phase and anti-phase), and cue direction (left and right retro-cue).

**Aim 6 (primary outcome):** Stimulation that is delivered in-phase to frontal and parietal cortex in the theta frequency is hypothesized to increased working memory capacity relative to anti-phase theta stimulation. Working memory capacity is quantified using Pashler's metric (see Aim 1). We will perform a two-way repeated-measures ANOVA with a between participants factor of TMS frequency (theta and alpha) and within-participants factor of TMS alignment (in-phase and anti-phase). We hypothesize to find a significant interaction ( $p < 0.05$ ) between TMS frequency and TMS alignment such that in-phase TMS in theta-frequency increases working memory capacity. Post-hoc t-tests will be performed using Tukey's method to control for multiple comparisons. *Sensitivity analysis:* Similar to aim 1, the impact of stimulation on hit rate, false alarm rate, and overall accuracy will be calculated. The robustness of these effects will be estimated using an individual differences analyses where baseline performance is used as a covariate to improve model estimation. Finally, the titration of working memory load by participant will be added as a covariate to explore if this factor changes the model estimation. These are framed as exploratory analyses.

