
of our a priori effect. Furthermore, these confirmatory sensitivity analyses avoid the multiple comparisons problem by relying on the initially established analyses.

**Aim 8 (secondary outcome):** Stimulation that is delivered in-phase is hypothesized to decrease the relative phase difference (phase lag) between the frontal and parietal cortex, whereas anti-phase stimulation is hypothesized to increase the phase lag. If stimulation entrained neural activity directly to the stimulation train, then this pattern of phase lag differences would be expected (because in-phase stimulation is delivered with zero phase lag and anti-phase stimulation is delivered with a phase lag). To calculate phase lag, first Morlet wavelet convolution is performed to extract instantaneous phase and amplitude for the frequency of interest for the two target sites. Next, the cross-spectral density is calculated (one signal multiplied by the complex conjugate of the other). From the cross-spectral density the phase angle is extracted, this is the phase lag. Then those phase lag values are averaged over the time frame of instance (here, the second half of the stimulation train). Finally, the angle of the resulting vector is taken to be the average phase lag. This metric quantifies the degrees of phase lag between the two target regions. Using a two-way ANOVA with factors for TMS frequency (theta or alpha) and TMS alignment (in-phase or anti-phase), we hypothesize a significant main effect ( $p < 0.05$ ) of TMS alignment such that phase lag is different between in-phase and anti-phase where in-phase decreases the phase lag and anti-phase increases the phase lag. We also hypothesize that this effect will be strongest for theta-frequency stimulation, which is hypothesized to be revealed as a significant main effect between TMS frequency and TMS alignment. Post-hoc t-tests will be performed using Tukey's method to control for multiple comparisons. *Sensitivity analysis:* Similar to Aim 7, the spread of stimulation effects in time, space, and frequency will be explored.

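### Aims 7 (primary) and 8 name a plain two-way ANOVA although frequency is between participants in phase two, and the text conflicts on whether phase one site is between or within

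*Combined protocol and SAP*

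**What the plan says.** **Phase two.** Section 4.1 randomizes participants to stimulation "in either theta or alpha frequency for both of the fourth and fifth session", so nobody receives both frequencies. Cue direction and alignment are mixed within a session. In Section 11.1, Aim 6 describes its ANOVA accordingly, "with a between participants factor of TMS frequency (theta and alpha) and within-participants factor of TMS alignment (in-phase and anti-phase". Aim 7 (primary) says "Using a two-way ANOVA with factors for TMS frequency (theta or alpha) and retro-cue direction (left or right" and Aim 8 (secondary) says "Using a two-way ANOVA with factors for TMS frequency (theta or alpha) and TMS alignment (in-phase or anti-phase". Neither calls the model repeated-measures, a term that Section 11.1 uses for each of Aims 1 to 6, and neither says which factor is between participants.

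All phase two outcomes are analysed after subtracting control: "in-phase minus arrhythmic-in-synchrony and anti-phase minus arrhythmic-independent". Section 11.1 also promises that "all statistical estimates of population parameters will be tabulated along with corresponding confidence intervals (CIs", and it reports any p above 0.05 as inconclusive.

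**Phase one.** The Study Summary labels the whole study parallel arms, and the phase one introduction in Section 11.1 uses the same label with location as a factor. Aim 1 then declares site and frequency both within-participant factors, and Section 4.1 describes a counter-balanced sequence of sites over sessions 4 and 5.

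**Sample size.** Section 3 states: "We will collect data until 48 participants have completed the final session for each phase". Section 11.2 derives the 48 from an effect size of 0.532 at 95% power, for the site-by-frequency interaction on working memory capacity.

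**The concern.** An ANOVA with one between and one within factor has two error terms: variation of within-person differences for the within factor and the interaction, and variation of person averages for the between factor. A plain two-way ANOVA pools both into one and counts each person's two values as two people. Two analysts could each claim to follow Aim 7 and obtain different p-values and intervals from the same data, on a primary outcome. The error term also decides whether a result is reported as inconclusive.

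The phase one conflict concerns the primary site-by-frequency test. A reader of the Study Summary or the Section 11.1 introduction would expect a comparison of two groups of people. A reader of Aim 1 and Section 11.2 would expect a paired test on 48 people.

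**Working it through.** **1. The plan's own figure.** For a paired t-test (equivalent to the interaction in a fully within-participant 2x2 ANOVA), two-sided 5%, standardized effect 0.532, noncentrality 0.532 x sqrt(n):
- n = 48 gives power 0.950 and n = 47 gives 0.946, so 48 is reproduced exactly.
- Section 11.2's other two figures also reproduce as paired: 0.83 gives 21 and 0.56 gives 44.
- Read as a two-group effect, 0.532 would need 93 per arm, 186 in total.

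The 95% power therefore belongs to a fully within-participant contrast.

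**2. Error terms for Aims 7 and 8.** Inputs: 48 completers, split 24 and 24 (1:1 is an assumption); two control-subtracted values per person, 96 in all; variance 1; within-person correlation r (not in the documents, so a range is shown).
- Plain ANOVA: error df = 96 - 4 = 92, expected mean square 1.
- Mixed ANOVA: 48 - 2 = 46 df for each error term.
- Interaction contrast: true variance = 2(1 - r) x 2/24 = (1 - r)/6. The plain ANOVA assumes 4/24 = 1/6. The ratio is 1 - r, and it is the same for the main effect of the within factor.
- Frequency main effect: true variance = (1 + r)/2 x 2/24 = (1 + r)/24. The plain ANOVA assumes 1/24. The ratio is 1 + r.

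As an approximation, the type I error of the interaction is 2 x [1 - Phi(1.986/sqrt(1 - r))]. At r = 0.3, 1.986/0.837 = 2.37, which gives 1.8%. Simulation, which lets the mean square vary, gives:

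| Assumed r | Type I error, interaction and within main effect | Interval width relative to correct (same tests) | Type I error, frequency main effect |
|---|---|---|---|
| -0.3 | 8.5% | 0.87 | 2.0% |
| 0 | 5.0% | 0.99 | 5.0% |
| 0.3 | 2.0% | 1.18 | 8.5% |
| 0.5 | 0.6% | 1.40 | 11% |

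The mixed error terms hold 5% throughout.

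**3. Which sign r has.** Subtracting control removes stable differences between people, so r may be small. It could be negative for Aim 8, which expects a pattern "where in-phase decreases the phase lag and anti-phase increases the phase lag". That requires the further assumption that people differ in how strongly they entrain, because opposite mean shifts alone do not make r negative.

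**4. What 48 means in phase two.** With 24 per arm, a frequency interaction has 95% power only for a difference between arms of 1.06 SD of the within-person difference score, and 80% power for 0.83 SD. The documents give no phase two effect size. Carrying over 0.532, which is an assumption, would give about 44%.

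**5. Phase one, side by side.** Parallel arms: the Study Summary and the Section 11.1 phase one introduction. Site within participants: Aim 1, and the sequence wording in Section 4.1. The wording for Aims 2, 3 and 5 does not settle it, because Section 11.1 also applies the term repeated-measures to Aim 6, which has a between factor.

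**The case against.** The strongest reply is that Aims 7 and 8 are under-specified rather than wrong. A two-way ANOVA can be a mixed one, Section 4.1 fixes frequency between participants, Aim 6 states the split for the same factor in the same phase, and Section 11.2 calls the design repeated-measures. A competent analyst would probably carry Aim 6 forward. That is fair, and the gap may be a simple omission. It remains that the two aims drop a term used for all six aims before them, and that the literal model gives wrong error bars for a primary outcome.

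It is also fair that the size is not known. Every figure depends on r, almost nothing is lost at r = 0, and the simulation uses normal values whereas Aim 8's outcome is an angle, so its figures are indicative.

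Two stronger readings are tempting:
- A reader might infer that Aim 7 will produce false positives, or that it simply loses power. Neither follows in general. The direction depends on the sign of r and is opposite for the within-person tests and the frequency main effect.
- A reader might infer that phase one site was in fact randomized between participants and that Aim 1 is underpowered, or conversely that the parallel-arms label is plainly wrong. The documents settle neither. A paired sample size shows how 48 was derived, not how people were randomized, and the change-log entry on parallel arms does not name a phase.

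**Conclusion.** The concern holds as a gap in the stated model and a conflict of design labels. For Aims 7 and 8, the ANOVA run as named has the wrong error term. With 24 per arm, and r between -0.3 and 0.5 taken as an assumption, type I error of the interaction and of the within-person main effect lies between about 8.5% and 0.6% instead of 5%. With positive r, intervals are too wide for those tests and too narrow for the frequency main effect.

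For phase one, the passages contradict each other and must be reconciled. If site is within participants, the analysis and power of Aim 1 stand and only the label changes. If site is between, Aim 1 cannot be fitted as written.

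On either reading, the stated 95% power at 48 does not extend to the phase two frequency interactions, because frequency there is between participants.

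**What to change.** 1. In Aims 7 and 8, name a mixed ANOVA, or an equivalent mixed model, with frequency between participants and cue direction (Aim 7) or alignment (Aim 8) within, as Aim 6 already does.
2. State once per phase in Section 11.1 which factors were randomized between participants and which vary within, and reconcile the Study Summary and the phase one introduction with Section 4.1 and Aim 1.
3. State in Section 11.2 that 95% power at 48 applies to a fully within-participant contrast. It does not cover the phase two frequency interactions, nor Aim 1 if phase one site proves to be between participants.
4. Only in that last case, make site a between factor in Aims 1, 2, 3 and 5.

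The cost is wording alone. The data and the analysis effort are unchanged.
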